7.3 Medications for Treatment of Infusion Reactions

Patients who experience infusion-associated symptoms may be treated symptomatically with acetaminophen, ibuprofen, diphenhydramine, and/or famotidine or another H2 receptor antagonist, as per standard practice. Serious infusion-associated events manifested by dyspnea, hypotension, wheezing, bronchospasm, tachycardia, reduced oxygen saturation, or respiratory distress should be managed with supportive therapies as clinically indicated (eg, supplemental oxygen and β_2 -adrenergic agonists).

7.4 Systemic corticosteroids and TNF-α inhibitors

Systemic corticosteroids and TNF- α inhibitors may attenuate potential beneficial immunologic effects of treatment with MPDL3280A but may be administered at the discretion of the treating physician after consultation with the Medical Monitor. If feasible, alternatives to corticosteroids should be considered. Premedication may be administered for Cycles ≥ 2 at the discretion of the

treating physician after consultation with the Medical Monitor. The use of inhaled corticosteroids and mineralocorticoids (eg, fludrocortisone) for patients with orthostatic hypotension or adrenocortical insufficiency is allowed. Megestrol administered as an appetite stimulant is acceptable while the patient is enrolled in the study.

7.5 Other Concomitant Medications

Influenza vaccination should be given during influenza season only (approximately October to March). Patients must not receive live, attenuated influenza vaccine (eg, FluMist[®]) within 4 weeks prior to first day of study treatment or at any time during the study but may receive inactivated vaccine.

Therapies considered necessary for the patient's well-being may be given at the discretion of the Investigator and should be documented on the eCRF. Other concomitant medications, except for analgesics, chronic treatments for concomitant medical conditions, or agents required for life-threatening medical problems, should be avoided.

Prophylactic antibiotics (eg, to prevent urinary tract infection or chronic obstructive pulmonary disease exacerbation) are allowed. Herbal and complementary therapies should not be encouraged because of unknown side effects and potential drug interactions, but any taken by the patient should be documented appropriately on the eCRF.

7.6 Excluded Therapies Concurrent with Rociletinib

7.6.1 Drugs that prolong QTc interval

Medications known to produce QT prolongation should be avoided during treatment of patients with rociletinib. See http://crediblemeds.org/ for the most up-to-date reference lists of QT-prolonging medications. Please note that the lists contain common supportive medications, such as anti-emetics (ondansetron [and other 5HT3 antagonists], metoclopramide, hydroxyzine), antibiotics (azithromycin, ciprofloxacin, metronidazole) and anti-depressants (escitalopram), which should not be used in combination with rociletinib.

Medications to consider for nausea that are not associated with QT prolongation include:

- Steroids (dexamethasone, methylprednisolone)
- Benzodiazepines
- Aprepitant
- Select anticholinergic agents (scopolamine)
- Trimethobenzamide
- Cannabinoids

Palonosetron is currently not listed on crediblemeds.org and a thorough QTc study showed no QTc effect. However, as rare cases of QTc prolongation have been reported, a more frequent ECG monitoring schedule should be adopted if used with rociletinib.

If a drug that has the potential to cause QT prolongation is indicated to control AEs (eg, 5HT3 inhibitor for nausea/vomiting), and the investigator believes that the patient is benefiting from rociletinib therapy, then additional ECGs should be performed to monitor for potential QT_C changes. The use of such concomitant medications and an appropriate ECG monitoring plan should be agreed between the Investigator and Sponsor.

7.6.2 CYP450 Isozyme Inhibitors and Inducers

Caution should be exercised in patients receiving oral rociletinib and requiring concomitant medication with warfarin (Coumadin), NSAIDs, or clopidogrel, as rociletinib moderately inhibited CYP2C8, CYP2C9, and CYP2C19 activities *in vitro*. Patients taking warfarin who are enrolled in the study are required to have international normalized ratio (INR) monitored regularly per standard clinical practice. Preliminary data from an ongoing definitive CYP inhibition study revealed that rociletinib also moderately inhibited CYP3A4. As such, caution should be exercised in patients receiving rociletinib and the following CYP3A4 substrates with narrow therapeutic range: alfentanil, astemizole, cisapride, cyclosporine, dihydroergotamine, ergotamine, fentanyl, pimozide, quinidine, sirolimus, tacrolimis, and terfenadine.

7.6.3 P-gp Substrates, Inhibitors and Inducers

Because rociletinib is a P-gp inhibitor *in vitro*, caution should be exercised in patients receiving PO rociletinib and requiring concomitant medication with digoxin, a P-gp substrate. Patients taking digoxin who are enrolled in the study are required to have digoxin levels monitored regularly via standard clinical practice.

Rociletinib is a P-gp substrate and thus, P-gp inhibitors have the potential to increase rociletinib exposure. As such, caution should be exercised in patients receiving rociletinib and the following P-gp inhibitors: amiodarone, azithromycin, captopril, carvedilol, clarithromycin, conivaptan, cyclosporine, diltiazem, dronedarone, erythromycin, felodipine, itraconazole, ketoconazole, lopinavir and ritonavir, quercetin, quinidine, ranolazine, verapamil.

Conversely, P-gp inducers have the potential to decrease rociletinib exposure. Caution should be exercised in patients receiving rociletinib and the following P-gp inducers: avasimibe, carbamazepine, phenytoin, rifampin, St. John's wort, and tipranavir/ritonavir.

7.6.4 Proton Pump Inhibitors

Because rociletinib is absorbed optimally in an acidic environment, proton pump inhibitors or H2 blockers should be used with caution. If gastric acid blockade is required, short acting antacids are preferred.

7.7 Excluded Therapies Concurrent with MPDL3280A

The following therapies are excluded while patients are receiving MPDL3280A and for 10 weeks after the last dose of MPDL3280A.

7.7.1 Denosumab

Patients who are receiving a RANKL inhibitor (denosumab) prior to enrollment must be willing and eligible to receive a bisphosphonate instead; denosumab could potentially alter the activity and the safety of MPDL3280A.

7.7.2 Immunomodulatory Agents

Patients are not allowed to receive immunostimulatory agents, including but not limited to IFN- α , IFN- γ , or IL-2. These agents, in combination with MPDL3280A, could potentially increase the risk for autoimmune conditions.

Patients should also not receive immunosuppressive medications, including but not limited to cyclophosphamide, azathioprine, methotrexate, and thalidomide. These agents could potentially alter the activity and the safety of MPDL3280A. Systemic corticosteroids and anti-TNF- α agents may attenuate potential beneficial immunologic effects of treatment with MPDL3280A but may be administered at the discretion of the treating physician after consultation with the Medical Monitor. If feasible, alternatives to these agents should be considered.

8 STUDY PROCEDURES

Table 1 summarizes the procedures and assessments to be performed for all patients.

Unless otherwise specified, all procedures and assessments in Cycle 2+ are to be completed within \pm 3 days of the scheduled time points relative to C1D1 of combination treatment with PO rociletinib and IV MPDL3280A. Perform assessments scheduled for C1D4 on that day (ie, no window) and assessments for C1D8 and C1D15 within \pm 2 days of the scheduled time points.

8.1 Screening Period

After written informed consent, patients will undergo screening assessments within 28 days before the first dose of study drug. Some assessments are required within 7 days (serum pregnancy test) or 14 days prior to the first dose of study treatment (see Table 1). A mandatory fresh tumor biopsy will be collected within 60 days prior to the first day of study treatment. If a biopsy was performed outside of the protocol within this 60-day period, and no intervening treatment was given, a repeat biopsy is not required if adequate tumor tissue can be provided to the Sponsor during the Screening Period. Other assessments performed before the patient signing of informed consent for this protocol are acceptable for the screening purposes of this protocol only if confirmed to have been standard of care. Please refer to Table 1 for details on assessments to be performed during the Screening Period.

Procedures required on Day 1 of Run-in-Period (Phase 1) or C1D1 (Phase 2) may be omitted if completed \leq 3 days earlier during the Screening Period.

8.2 Treatment Period

Before enrollment of a patient, all eligibility criteria must be satisfied, and enrollment must be approved by the Sponsor's medical monitoring team.

The Treatment Period will consist of 21-day combination treatment cycles, with MPDL3280A administered by IV infusion on the first day of each cycle, beginning with C1D1, and rociletinib administered PO BID continuously. During Phase 1 of the study only, the Treatment Period will also include a 7-day Run-in Period of rociletinib monotherapy prior to C1D1 of combination treatment with rociletinib and MPDL3280A. Study visits will be scheduled as indicated in Table 1. Additional clinic visits will also occur as clinically indicated.

During the Treatment Period, tumor assessments will be conducted every 2 cycles (6 weeks ± 1 week) through Cycle 6 (ie, at the end of Cycles 2, 4, and 6); every 3 cycles (9 weeks ± 1 week) after Cycle 6 (ie, at the end of Cycles 9, 12, etc); and at the EOT Visit. The frequency of tumor assessments may be further reduced after 2 years with approval of the Medical Monitor (see Section 8.4.3 for details). Tumor scans will be evaluated locally for response evaluation and treatment decision-making.

Patients will be allowed to continue on study as long as they experience no unacceptable toxicities and they continue to receive clinical benefit from the study treatment as assessed by the

Investigator (with agreement from the Sponsor's Medical Monitor) or until the patient meets any of the withdrawal criteria (see Section 11 for details and exceptions).

8.2.1 Post-Progression Treatment

Patients may continue to receive treatment with rociletinib and/or MPDL3280A after radiographic progression of disease if, in the opinion of the Investigator and approved by the Sponsor, the patient is still benefiting from treatment. This must be discussed with the Sponsor's Medical Monitor and will be reviewed on a case-by-case basis. If a patient continues treatment post-progression, all study assessments including efficacy assessments, safety assessments, and blood collection for biomarker analysis, should continue per protocol. The patient should be discontinued from treatment once it is clear that no further clinical benefit can be achieved.

The criteria below are required for treatment post-progression:

- Evidence of clinical benefit as assessed by the Investigator;
- Absence of symptoms and signs (including worsening of laboratory values [eg, new or worsening hypercalcemia]) indicating unequivocal progression of disease;
- No decline in ECOG performance status that can be attributed to disease progression;
- Absence of tumor growth at critical anatomical sites (eg, leptomeningeal disease) that cannot be managed by protocol-allowed medical interventions;
- Patients for whom approved therapies exist must provide written consent to acknowledge deferring these treatment options in favor of continuing study treatment at the time of initial apparent progression;
- Written Sponsor approval for treatment post-progression;
- Patients in whom radiographic disease progression is confirmed at a subsequent tumor assessment may be considered for continued study treatment at the discretion of the Investigator if they continue to meet the criteria above and have evidence of clinical benefit.

8.2.2 End-of-Treatment Visit

Patients will be asked to return to the clinic for the EOT Visit 28 days (+7 days) after the last dose of study treatment, or before the patient initiates another anticancer agent (if sooner), to assess safety of the patients. Safety evaluation assessments for the EOT Visit are outlined in Table 1. All AEs (including SAEs and protocol-defined events of special interest), regardless of attribution, will be recorded until 28 days after the last dose of study treatment or until initiation of another anticancer therapy, whichever occurs first. Ongoing AEs considered related to study treatment and all SAEs, regardless of causality, will be followed until the event has resolved to baseline grade, the event is assessed by the Investigator as stable, new anticancer treatment is initiated, the patient is lost to follow up, the patient withdraws consent, or it is determined that the study treatment or participation is not the cause of the AE.

Tumor assessment scans do not need to be repeated if radiographic disease progression has been documented previously or the last scans were performed < 2 weeks before the last dose of study treatment or the patient had disease progression at the last scan. For patients who provide additional consent, an optional fresh tumor biopsy will be collected at the time of permanent treatment discontinuation due to disease progression (at the time the Investigator believes the patient is no longer deriving clinical benefit from study treatment, if treatment beyond radiographic disease progression is approved). This optional biopsy and associated blood samples scheduled for the EOT Visist (see Table 2) should occur as close as possible to the date of the decision to permanently discontinue study.

8.3 Follow-Up Period

During the Follow-Up-Period, all patients will be contacted by the site every 12 weeks $(\pm 1 \text{ week})$ for the collection of information on all subsequent anticancer therapy and for the monitoring of survival status until the patient's death, patient withdrawal of consent, or a decision by the Sponsor to cease data collection and close the study, whichever comes first. These assessments may be performed during routine clinic visits or by telephone contact.

8.4 Methods of Data Collection

8.4.1 Patient History

Patient information collected during screening will include basic demographics; medical history, including smoking status, medical conditions, and oncology history including date of cancer diagnosis, prior cancer treatment, and any surgical procedures. For patients being considered for enrollment in the study, screening assessments will not begin until patient tumor EGFR mutation status is determined through local assessments.

8.4.2 Safety Evaluations

8.4.2.1 Adverse Event Assessment

The Investigator has the responsibility for assessing the safety of the patients and patient compliance with the protocol to ensure study integrity. Patients will be monitored for AEs from the time of the first dose of study drug is administered through 28 days after the last dose of study drug. Study procedure-related AEs that occur after signing of the Informed Consent Form (ICF) and before administration of rociletinib and MPDL3280A will also be collected. All ongoing AEs related to study treatment and all SAEs, and all protocol-defined events of special interest (Section 9.6) will be followed until resolution or stabilization. Adverse events and laboratory abnormalities will be graded according to the NCI CTCAE grading system (v4.03).

Complete details for monitoring and managing AEs, including the definition of study drug-related AEs, are provided in Section 9.

8.4.2.2 Clinical Laboratory Investigations

Blood for safety evaluations will be analyzed by a local laboratory to inform patient treatment decisions, and results must be reviewed by the Investigator before administration of rociletinib and/or MPDL3280A. Additional tests may be performed at the Investigator's discretion. The panels of laboratory tests to be performed are shown below:

Hematology: Hematology assessments include hemoglobin, hematocrit, WBC and differential (with ANC), reticulocyte count, and platelet count. Hematology results must be reviewed by the Investigator before administration of rociletinib and/or MPDL3280A.

Patients known to require concomitant therapy with anticoagulants such as warfarin should also have INR monitored throughout the study.

Serum Chemistry: Serum chemistry assessments include total protein, albumin, creatinine, BUN or urea, total bilirubin, alkaline phosphatase, ALT, AST, total cholesterol, fasting glucose, sodium, potassium, magnesium, chloride, calcium, phosphorus and uric acid.

In addition separate assessments of fasting glucose; hemoglobin A1c; TSH and free T_3 and T_4 ; will be performed as described in Table 1.

Urinalysis: Urinalysis will be performed on freshly voided clean sample by dipstick for protein, glucose, blood, pH, and ketones per the schedule of evaluations. If dipstick findings are abnormal, then a microscopic evaluation will be performed to assess the abnormal findings. Urinalysis is scheduled at screening only.

Serum ß-hCG Pregnancy Test (Local Lab): Performed on females of childbearing potential \leq 7 days before first day of study treatment and at the EOT Visit. If the serum pregnancy test results are not available on first day of study treatment, a urine pregnancy test can be performed on first day of study treatment to confirm that the patient is not pregnant before dosing. A negative result must be confirmed by a physician before the first dose of either study drug can be administered. Both values should be entered in the eCRF.

Laboratory reports will be reviewed by the Investigator or delegated physician who will then comment on out-of-range parameters and assess clinical significance. Clinically significant abnormalities and associated panel results, as well as results of any additional tests performed as follow up to the abnormalities, will be documented on the eCRF as an AE.

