	especially during screening for study eligibility purposes. Additional consideration should be given to borderline ECOG performance status to avoid enrolling patients
	with significant impairment.
J	After the patient has been resting for at least 5 minutes, measure body temperature, heart rate, respiratory rate, and blood pressure. For the first infusion of
	MPDL3280A, measure vital signs within 60 minutes before, every 15 (\pm 5) minutes during the infusion, and 30 (\pm 10) minutes after the infusion. For subsequent
	infusions, vital signs will be collected within 60 minutes before the infusion, during the infusion if clinically indicated or if symptoms occurred in the prior infusion,
	and 1 hour $(\pm 10 \text{ minutes})$ after the infusion.
K	Includes hemoglobin, hematocrit, WBC and differential (with ANC), reticulocyte count, and platelet count. Hematology results must be reviewed by the Investigator
_	before administration of rociletinib and/or MPDL3280A.
L	Includes prothrombin time, international normalized ratio (INR), and activated partial thromboplastin time (aPTT). Patients known to require concomitant therapy
	with anticoagulants such as warfarin should also have INR monitored throughout the study.
Μ	Collect a freshly voided, clean sample and analyze by dipstick for protein, glucose, blood, pH, and ketones. If dipstick findings are abnormal, then a microscopic
	evaluation will be performed to assess the abnormal findings.
Ν	Includes total protein, albumin, creatinine, blood urea nitrogen (BUN) or urea, total bilirubin, alkaline phosphatase, alanine aminotransferase (ALT), aspartate
	aminotransferase (AS1), total cholesterol, tasting glucose, sodium, potassium, magnesium, chloride, calcium, phosphorus and uric acid. Fasting glucose must be
	measured after an 8-hour fast (no food or liquid other than water).
0	Fasting glucose must be measured after an 8-hour fast (no food or liquid other than water).
Р	Perform for females of childbearing potential \leq /days before first day of study treatment and at the EOT Visit. If the serum pregnancy test results are not available on
	the first day of study treatment, a urine pregnancy test can be performed on the first day of study treatment. A negative result must be confirmed by a physician before
	the first dose of study treatment.

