There were 11 deaths on study, including the 28-day post-treatment period after the last dose of rociletinib. Eight deaths were reported as due to progression of NSCLC, one death due to pulmonary embolism, one death due to pneumonia, and one death of unknown cause. A causal relationship with rociletinib could not be ruled out for the death of unknown cause; all other deaths were reported as unrelated to study drug.

Table 3: Treatment-Related Serious Adverse Events Reported by Patients in Study CO-1686-008

System Organ Class Preferred Term	< 900 BID FB (N = 38)	900 BID FB (N = 19)	500 BID HBr (N = 18)	625 BID HBr (N = 17)	750 BID HBr (N = 50)	1000 BID HBr (N = 6)	Overall (N = 148)
Number of patients with	at least 1 treatment	-related treatment-	emergent SAE				
Overall	4 (10.5%)	1 (5.3%)	4 (22.2%)	3 (17.6%)	4 (8.0%)	1 (16.7%)	17 (11.5%)
Cardiac Disorders	•	•	•	•	•		•
Pericarditis	1 (2.6%)	0	0	0	0	0	1 (0.7%)
Gastrointestinal Disor	ders	•	•	·	·		•
Diarrhea	1 (2.6%)	1 (5.3%)	0	0	0	0	2 (1.4%)
Nausea	1 (2.6%)	0	1 (5.6%)	0	1 (2.0%)	0	3 (2.0%)
Pancreatitis	0	0	1 (5.6%)	0	0	0	1 (0.7%)
Vomiting	2 (5.3%)	0	1 (5.6%)	0	1 (2.0%)	0	4 (2.7%)
Infections and Infestation	ns	•	•	·	·		•
Gastroenteritis	0	0	0	0	1 (2.0%)	0	1 (0.7%)
Investigations	•	•	•	·	·		•
ECG QT prolonged	0	0	0	1 (5.9%)	1 (2.0%)	0	2 (1.4%)
ECG T wave inversion	0	0	0	0	1 (2.0%)	0	1 (0.7%)
Transaminases increased	0	1 (5.3%)	0	0	0	0	1 (0.7%)
Metabolism and Nutri	tion Disorders						
Combined terms of hyperglycemia	1 (2.6%)	0	4 (22.2%)	1 (5.9%)	2 (4.0%)	1 (16.7%)	9 (6.1%)
Decreased appetite	0	1 (5.3%)	0	0	0	0	1 (0.7%)
Hypoglycemia	1 (2.6%)	0	0	0	0	0	1 (0.7%)
Hypokalemia	0	0	0	1 (5.9%)	0	0	1 (0.7%)
Respiratory, Thoracic, a	nd Mediastinal diso	rders					
Pneumonitis	0	0	0	1 (5.9%)	0	0	1 (0.7%)

BID, twice daily; ECG, electrocardiogram; FB, rociletinib free base; HBr, rociletinib hydrobromide; N, number of patients; SAE, serious adverse event.

Treatment-Related Adverse Events (AEs): The most frequently reported treatment-related AEs (all grades, $\geq 20\%$ of patients) were hyperglycemia (33%; including Medical Dictionary for Regulatory Activities [MedDRA] Preferred Terms blood glucose elevated, glucose tolerance impaired, and hyperglycemia), nausea (28%), and fatigue (20%). Treatment-related AEs reported by at least 5% of patients are summarized in Table 4. The majority of AEs were mild or moderate in severity.

Other Treatment-Related Adverse Events of Interest

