 - Grade ≥ 3 hyperglycemia lasting ≤ 7 days. Grade > 3 hyperglycemia will be considered a DLT only if it lasts for more than 7 days despite optimized antihyperglycemic treatment (eg, oral anti-hyperglycemic therapy);
 - Grade ≥ 3 elevation of serum creatine kinase (CK) level that is asymptomatic (ie, not accompanied by signs, symptoms, or other laboratory abnormalities associated with rhabdomyolysis or myocardial injury) that is deemed by the Investigator to be clinically insignificant and that returns to Grade ≤ 2 within 7 days.

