6.2.7 Management of Potential Pancreatic Toxicity

Symptoms of abdominal pain associated with elevations of amylase and lipase, suggestive of pancreatitis, have been associated with the administration of other immunomodulatory agents.
The differential diagnosis of acute abdominal pain should include pancreatitis. Appropriate workup should include an evaluation for obstruction, as well as serum amylase and lipase tests.

Pancreatic toxicity should be managed according to Table 16.

 Table 16:
 Management Guidelines for Amylase/Lipase Abnormalities

Description	Management
Amylase/lipase (> ULN and $\leq 2 \times$ ULN) and asymptomatic	Continue MPDL3280A;Monitor amylase/lipase levels prior to dosing.
Amylase/lipase (> $2 \times ULN$ to $\leq 5 \times ULN$) and asymptomatic	 Continue MPDL3280A; Monitor amylase/lipase weekly; Consider oral prednisone 10 mg daily or equivalent for prolonged elevation (eg, more than 3 weeks).
Amylase/lipase (> 5 × ULN) and asymptomatic	 Hold MPDL3280A; Monitor amylase/lipase every other day and consider oral prednisone 60 mg daily or equivalent; Consult a gastroenterologist; Resume MPDL3280A dosing when lipase/amylase levels are less than 2 × ULN.
Autoimmune pancreatitis (abdominal pain and raised amylase/lipase levels)	 Hold MPDL3280A; Consult a gastroenterologist; Consider administering IV steroids (prednisone equivalent of 60 mg/day) followed by taper over 2-4 weeks; Resume MPDL3280A when enzyme levels are less than 2 × ULN and patient is asymptomatic; Permanently discontinue MPDL3280A for life threatening immune related pancreatitis.

IV, intravenous; ULN, upper limit of normal.

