	 Discussion between the Investigator and Medical Monitor and approval to restart dosing is required before rociletinib or MPDL3280A are restarted.
	 Permanently discontinue MPDL3280A for life-threatening immune-related pulmonary events.

Clovis Oncology, Inc. Rociletinib (CO-1686) FINAL Version 1.0

Toxicity	Attribution to both agents	
Amylase/Lipase	Grade ≥ 3 amylase/lipase elevation	
	 Delay MPDL3280A and rociletinib for asymptomatic Grade ≥ 3 amylase and/or lipase elevations and monitor QOD until decreasing; for Grade 4 elevations consider 10 mg prednisone daily; 	
	 If symptomatic, MPDL3280A and rociletinib should be held. Methylprednisolone or oral steroids (prednisone equivalent of 60 mg/day) should be administered. Rociletinib dosing may be restarted when symptoms resolve and the amylase/lipase elevation is Grade ≤ 1. If no recurrent symptoms after 14 days then MPDL3280A dosing may be reinitiated at the same dose level. 	
	 If the Grade ≥ 3 amylase/lipase elevation recurs with symptoms before MPDL3280A re-initiation then rociletinib should be permanently discontinued. 	
	 If the Grade ≥ 3 amylase/lipase elevation recurs with symptoms after MPDL3280A re-initiation then rociletinib should be held until amylase/lipase elevation is Grade ≤ 1 and the MPDL3280A permanently discontinued. 	
	 MPDL3280A should be permanently discontinued for life-threatening, immune-related pancreatitis. 	
Hypothyroidism	 No change in MPDL3280A dosing will be implemented for asymptomatic TSH elevation; start thyroid replacement hormone and monitor TSH weekly; 	
	 Delay MPDL3280A for symptomatic TSH elevation; start thyroid replacement hormone and monitor TSH weekly; resume MPDL3280A when symptoms improve and TSH is decreasing. 	

AE, adverse event; ALT, alanine aminotransferase; AST, aspartate aminotransferase; IV, intravenous; NSAID, nonsteroidal anti-inflammatory drug; QOD, every other day; TSH, thyroid-stimulating hormone; ULN, upper limit of normal.

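### Tables 16 and 18 act on asymptomatic amylase/lipase elevations, but no scheduled panel measures either enzyme, so the rules will not be triggered systematically

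*Combined protocol and SAP*

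**What the plan says.** The scheduled laboratory content is given twice. Section 8.4.2.2 states: "Serum chemistry assessments include total protein, albumin, creatinine, BUN or urea, total bilirubin, alkaline phosphatase, ALT, AST, total cholesterol", then fasting glucose, then "sodium, potassium, magnesium, chloride, calcium, phosphorus and uric acid". It continues: "In addition separate assessments of fasting glucose; hemoglobin A1c; TSH and free" T3 and T4. Table 1, footnote N, repeats the chemistry list, beginning "Includes total protein, albumin, creatinine, blood urea nitrogen (BUN) or urea, total bilirubin, alkaline phosphatase, alanine aminotransferase (ALT". Section 8.4.2.2 also lets the investigator order further tests at discretion.

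The rules that use the missing analytes are elsewhere:

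- Section 6.2.7, Table 16, has four rows. Three concern asymptomatic amylase/lipase elevation: above ULN up to 2 × ULN, above 2 up to 5 × ULN, and above 5 × ULN. The lowest band says "Monitor amylase/lipase levels prior to dosing". The highest holds MPDL3280A. The text above the table makes both enzymes part of the workup of acute abdominal pain.
- Section 6.3, Table 18, lists amylase/lipase as an overlapping toxicity. It delays both drugs for asymptomatic Grade 3 or higher "amylase and/or lipase elevations and monitor QOD until decreasing".
- Section 3.2.1 lists, among the exceptions to the organ-toxicity DLT criterion, a Grade 3 or higher "elevation of serum creatine kinase (CK) level that is asymptomatic". The exception applies if the investigator judges the elevation clinically insignificant and it returns to Grade 2 or lower within 7 days.

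Section 9.6 names pancreatitis as an event of special interest for MPDL3280A. Section 1.3.1, Table 3, includes "Pancreatitis" among the treatment-related serious events seen with rociletinib.

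**The concern.** A rule for an asymptomatic laboratory abnormality needs a test that is done without symptoms. Here the schedule provides none, at screening or on treatment, and no eligibility criterion asks for one. Table 16's pre-dose monitoring does not fill the gap, because it starts only once an elevation is known. The abdominal-pain workup does not fill it either, because it is prompted by a symptom.

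Two things are at stake. First, the planned holds and delays for silent enzyme elevation would operate at some sites and not at others. Second, the reported frequency of such elevations would depend on testing habit. Under Section 9.4, a laboratory value becomes an adverse event if it leads to action on study drug, needs intervention or is judged clinically significant. A value that is never measured can do none of these. Treatment-emergent adverse events are a Phase 1 primary endpoint, so differences between cohorts or phases in this item could reflect who was tested.

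**Working it through.** No sample size or power figure is involved. The check compares each rule with the scheduled source of the value it needs.

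**Panel count (Section 8.4.2.2; Table 1, footnote N).** Nine analytes from total protein to total cholesterol, one fasting glucose, seven from sodium to uric acid: 9 + 1 + 7 = 17. Amylase, lipase and CK among them: 0 of 3. Other laboratory rows of Table 1 (hematology, coagulation, urinalysis, fasting glucose, pregnancy test, HbA1c, thyroid tests, viral serology): also none.

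**Rules against sources.**

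| Rule | Value needed | Scheduled source |
|---|---|---|
| Table 9, QTc | ECG | ECG row of Table 1 |
| Table 10, hyperglycemia | fasting glucose | chemistry panel, plus C1D4, C1D8, C1D15 |
| Table 13, liver tests | AST, ALT, bilirubin | chemistry panel |
| Table 15, asymptomatic TSH rise | TSH | screening, then every 3 months (footnote Q) |
| Table 16, asymptomatic rows | amylase, lipase | none |
| Table 18, amylase/lipase | amylase, lipase | none |
| Section 3.2.1, CK exception | CK, with a repeat to show recovery within 7 days | none |

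The four comparable rules each have a scheduled test behind them. The enzyme rules do not, which suggests an omission more than a choice.

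**What the asymptomatic rows require.** Of the three in Table 16, two continue MPDL3280A with monitoring and one holds it. Table 18 adds the delay of both drugs.

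**Background frequency (Table 3).** Treatment-related serious pancreatitis: 1/18 = 5.6% at 500 mg BID HBr, the first Phase 1 cohort's dose here. Overall it was 1/148 = 0.7%, and at the higher HBr doses 0/(17 + 50 + 6) = 0/73. The documents give no rate for silent enzyme elevation.

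**Timing of existing chemistry draws (Table 1).** These are screening, Run-in Day 1 (Phase 1), C1D1, Day 1 of each later cycle, and EOT. C1D4, C1D8 and C1D15 carry fasting glucose but no chemistry panel. Footnote A puts assessments before dosing, so the C1D1 draw precedes the first MPDL3280A infusion. The next draw is C2D1, nominally Day 1 + 21 = Day 22, with a window of ±3 days (Day 19 to Day 25). The DLT period is the first 21 days of combination treatment. As scheduled, no chemistry draw falls inside it after the first infusion; only an early C2D1 visit could.

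**The case against.** The strongest reply is that Tables 16 and 18 are guidance for a result already in hand. Section 6.2.7 concerns a potential toxicity, reported with other immunomodulatory agents, and the protocol leaves routes to a value: discretionary tests and the abdominal-pain workup. That is fair as far as it goes. A reader might infer that the rules cannot trigger at all; the documents do not support this. What stands is that neither route is systematic, and the symptom-driven one largely misses the patients the asymptomatic rows describe.

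A reader might also infer that the missing baseline disables the rules. It does not. The triggers are multiples of ULN or CTCAE grades, and the stated resumption limits (below 2 × ULN, or Grade 1 or lower) need no baseline.

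A third tempting reading is that a missed enzyme DLT would distort dose finding, for example by turning 1/3 (stay) into 0/3 (escalate) in Appendix H. This is not supported:

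- Table 5 plans only 500 mg and 375 mg, starting at 500 mg, so there is no planned higher dose.
- Section 3.2.2 continues until at least 6 patients are treated at one dose or 18 are enrolled in Phase 1, and both 0/6 and 1/6 read as escalate.
- Section 3.2.1 requires a DLT to be clinically significant and exempts asymptomatic Grade 3 laboratory values judged not significant.
- The CK item is an exception that keeps an event from counting; it does not trigger a DLT or a hold.

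Finally, the single pancreatitis event is thin evidence: a serious clinical event says little about silent elevations, and none occurred at the higher HBr doses. It shows only that the organ is relevant.

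**Conclusion.** The point holds for amylase and lipase. The protocol sets actions for asymptomatic elevations, including one hold and one delay of both drugs, and schedules zero measurements of either enzyme. The rules will therefore not be triggered systematically, and detection will vary by site, although pancreatitis is an event of special interest and amylase/lipase is a listed overlapping toxicity. CK has the same gap in weaker form: without a scheduled value, its conditional exception cannot be checked consistently.

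The size is a count of missing measurements. How many elevations would go unseen cannot be estimated from the documents. The conclusion assumes that sites follow Table 1 as written and that no separate laboratory instruction adds these tests. It does not affect the Phase 2 response endpoint, and no effect on the Phase 1 dose decision is shown. It is worth correcting because the safety rules and the data they need do not match and the remedy is inexpensive.

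**What to change.** Reconcile the laboratory schedule (Table 1, footnote N; Section 8.4.2.2) with the rules that depend on it (Table 16, Table 18, and the CK exception in Section 3.2.1). The sponsor should settle which text changes.

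A low-cost way is to add amylase and lipase to the chemistry draws already scheduled, and CK as well if its exception is meant to be checkable, and to include them in the laboratory summaries of Section 10.2.5.3. All thresholds and hold rules stay as written. If the sponsor instead intends the rules to apply only to values obtained for other reasons, Tables 16 and 18 should say so, and the report should give the number of patients tested beside any frequency.

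The cost of the added analytes is a small assay charge on existing samples and some incidental elevations that would then fall under the protocol's own rules, including its holds and steroid considerations. The amendment should not claim better Phase 1 DLT ascertainment from these draws: as scheduled they do not sample the DLT period after the first infusion, and they cannot verify a 7-day CK recovery.
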